#### 9.6.9 Efficacy Evaluations

Not applicable.

# 9.7 TREATMENT, SUBJECT, SITE, AND STUDY DISCONTINUATION

# 9.7.1 Study Drug Discontinuation

Premature discontinuation of the study drug by the Investigator should be discussed whenever possible with the Medical Monitor before the subject stops taking the study drug.

Potential reasons for permanent discontinuation of the study drug are detailed in Section 9.7.2.1. The primary reason for study drug discontinuation should be documented on the appropriate eCRF along with the date of stopping the study drug, and the total amount of the study drug taken. If the study drug is discontinued, regardless of the reason, the end-of-treatment evaluations are to be performed as completely as possible.

# 9.7.2 Withdrawal of Subjects from the Study

A subject may voluntarily withdraw from the study at any time for any reason without prejudice to their future medical care by the physician or at the institution. In addition, the Investigator or Sponsor may withdraw the subject at any time (e.g., in the interest of subject safety).

To the extent feasible, all withdrawn subjects should undergo the protocol-specified post-treatment follow-up. However, subjects will not be followed for any reason after consent has been withdrawn.

The reason for withdrawal from the study must be determined by the Investigator and recorded in the subject's medical record and on the eCRF. If a subject is withdrawn for more than one reason, each reason should be documented in the source document and the most clinically relevant reason should be entered on the eCRF. If an AE is (one of) the reason(s) for discontinuation, then "Adverse event" must be recorded as the reason for discontinuation on the eCRF. Any comments (spontaneous or elicited) pertinent to the withdrawal or complaints made by the subject must be recorded in the source documents.

#### 9.7.2.1 Reasons for Study Drug Discontinuation and Withdrawal

Reasons for discontinuation from the study drug and for withdrawal from the study include but are not limited to:

- Adverse event
- Any medical condition that may jeopardize the subject's safety
- Significant worsening in the subject's underlying condition
- Withdrawal of consent by the subject
- Protocol violation (such as subject non-compliance with the study drug or study procedures, use of prohibited medication)
- Subject lost to follow-up
- Pregnancy.

For any subject lost to follow-up, at least three documented attempts must be made to contact the subject prior to the last protocol-mandated study visit. One of these documented attempts must include a written communication sent to the subject's last known address via courier or mail with an acknowledgement of receipt request.

# 9.7.2.2 Replacement of Subjects

Subjects prematurely discontinuing study drug or withdrawing from the study (while on treatment or during the 2-week post-treatment safety follow-up) may be replaced if the following criteria are met:

- If a subject discontinues study drug or withdraws from the study for any reason on or before Day 22.
- If a subject misses a visit(s) due to non-compliance, SAE and/or hospitalization at a critical PK and/or biomarker timepoint(s) as it relates to the study endpoint.

A decision to replace subject(s) will be determined by the Sponsor and communicated to the Principal Investigator/Site with rationale and further instruction, as applicable.

# 9.7.3 Study Discontinuation

The Sponsor has the right to terminate this study at any time. The Sponsor will notify the investigator(s) in case a decision is made to discontinue the study.

# 9.7.4 Site Discontinuation

The Sponsor has the right to close a site at any time. Reasons for closing a site may include, but are not limited to, the following:

- Excessively slow recruitment
- Poor protocol adherence
- Inaccurate or incomplete data recording
- Non-compliance with the International Council for Harmonization (ICH) guideline for Good Clinical Practice
- Study activities completed (i.e., all subjects have completed the study and all obligations have been fulfilled.).

# 10. ASSESSMENT OF SAFETY

#### 10.1 DEFINITIONS

An **Adverse Event (AE)** is any untoward medical occurrence in a clinical investigation subject administered a pharmaceutical product and that does not necessarily have a causal relationship with this treatment. An AE can therefore be any unfavorable and unintended sign (including an abnormal laboratory finding), symptom, or disease temporally associated with the use of a

medicinal (investigational) product, whether related to the medicinal (investigational) product or not (ICH Guidance E2A 1994).

**Treatment-emergent AEs** are defined as any AE with an onset between the first dose of the study drug and the last study visit, or any AE with an onset prior to first dose that increases in severity or frequency after the first dose of study drug.

A **Serious Adverse Event (SAE)** is any untoward medical occurrence (whether considered to be related to investigational product or not) that at any dose:

- Results in death
- Is life-threatening [1]
- Requires inpatient hospitalization or prolongation of existing hospitalization [2]
- Results in persistent or significant disability/incapacity
- Is a congenital abnormality/birth defect
- Is an important medical event [3]
  - [1] The term 'life-threatening' in the definition of 'serious' refers to an event in which the subject was at risk of death at the time of the event; it does not refer to an event which hypothetically might have caused death if it was more severe.
  - [2] Hospitalizations which are the result of elective or previously scheduled surgery for pre-existing conditions, where such conditions have not worsened after initiation of treatment, should not be classified as SAEs. For example, an admission for a previously scheduled ventral hernia repair would not be classified as an SAE. However, complication(s) resulting from a hospitalization for an elective or previously scheduled surgery that meets serious criteria must be reported as SAE(s).
  - [3] Important medical events that may not result in death, be life-threatening, or require hospitalization may be considered an SAE when, based upon appropriate medical judgment, they may jeopardize the subject and may require medical or surgical intervention to prevent 1 of the outcomes listed in this definition. Examples of such medical events include allergic bronchospasm requiring intensive treatment in an emergency room or at home; blood dyscrasias or convulsions that do not result in inpatient hospitalization; or the development of drug dependency or drug abuse.

#### Note:

The terms "severe" and "serious" are not synonymous. Severity refers to the intensity of an adverse event (e.g., rated as mild, moderate, or severe; see Section 10.3.3.1); the event itself may be of relatively minor medical significance (such as severe headache without any further findings). Severity and seriousness need to be independently assessed for each adverse event recorded on the eCRF.

Adverse events of special interest (AESI): An adverse event of special interest (serious or non-serious) is one of scientific and medical concern specific to the sponsor's product or program, for which ongoing monitoring and rapid communication by the investigator to the sponsor can be appropriate. Such an event might warrant further investigation in order to characterize and understand it. Depending on the nature of the event, rapid communication by the trial sponsor to other parties (e.g., regulators) might also be warranted.

The following events will be considered AESIs in this study:

• Treatment-emergent ALT or AST >3 x upper limit of normal (ULN) in combination with (1) total bilirubin >2 x ULN and/or (2) clinical jaundice.

Clinically significant laboratory, ECG, or vital signs abnormalities: A laboratory test or ECG abnormality is deemed clinically significant if it meets one or more of the following criteria:

- Is accompanied by clinical symptoms
- Results in a change in study treatment (e.g., study drug interruption or discontinuation, or dosage modification)
- Results in a medical intervention (e.g. treatment) or a change in concomitant therapy
- Is clinically significant in the investigator's judgment.

**Study Drug Misuse** is defined as intentional use of the investigational product other than as directed or indicated at any dose (Note: this includes a situation where the investigational product is not used as directed at the dose prescribed by the protocol).

**Overdose** is an intentional or unintentional intake of a dose of the investigational product exceeding the pre-specified total daily dose of the product.

**Medication Error** is an error made in prescribing, dispensing, administration, and/or use of an investigational product.

#### 10.2 OVERALL SAFETY PLAN

The safety plan for this study is based on clinical experience with MK-7 in published clinical studies. The anticipated safety risks for EPN-701 are outlined in Section 6.3.4. Please refer to the EPN-701 Investigator's Brochure for a complete summary of clinical safety information.

Several measures will be taken to ensure the safety of subjects participating in this study. These include the pre-specified eligibility criteria (see Section 9.1.1 and Section 9.1.2), designed to exclude subjects at higher risk for adverse events, close safety monitoring of subjects during the study (see Section 9.5), including assessment of the nature, frequency, and severity of adverse events (see Section 10.3).

General safety assessments will consist of monitoring and recording adverse events, including SAEs, AESIs, and AEs leading to study drug discontinuation (with or without withdrawal from the study), performing protocol specified physical examinations, ECGs and safety laboratory assessments (including hematology, CMP, and coagulation panel), and measuring vital signs; see **Table 1** for the list and timing of study assessments. During on-treatment study visits, applicable clinical and laboratory assessments will be completed and reviewed prior to study drug administration. Adverse events (regardless of relationship to study drug) will be recorded in the AE CRF for 14 days after the last dose of EPN-701 (until the EOS Visit/Day 29), and will be graded by severity, and assessed for causality. Serious adverse events (SAEs), AESIs and pregnancies occurring during or within 30 days after the last dose of EPN-701 will be reported in an expedited

fashion, as described in Section 10.4. Any case of study drug error, misuse, or overdose will also be reported in an expedited fashion (see Section 10.4).

A SRC will review the safety data accumulated during the study at regular intervals. The SRC will be comprised of the Sponsor's Medical Monitor, Independent Medical Monitor, and the Principal Investigator; refer to Section 10.6.

# 10.2.1 Dose Modifications and Interruptions due to Adverse Events

Dose reduction of EPN-701 is not permitted in this study.

There are currently no known adverse events that would require interruption or discontinuation of EPN-701 treatment. However, unanticipated adverse events or other safety findings during the trial may warrant interruption or discontinuation of study drug. The acceptable length of interruption will depend on agreement between the investigator and the Medical Monitor.

#### 10.3 RECORDING AND ASSESSMENT OF ADVERSE EVENTS

The investigator is responsible for ensuring that all adverse events are recorded on the Adverse Event eCRF and reported to the Sponsor in accordance with instructions provided in this section and in Section 10.4 (immediate reporting).

For each adverse event, the investigator will make an assessment of seriousness (see Section 10.1 for seriousness criteria), severity (see Section 10.3.3.1), and causality (see Section 10.3.3.2) on the Adverse Event eCRF.

# 10.3.1 Adverse Event Recording and Reporting Period

All AEs with an onset between the time the informed consent is signed and 14 days after the last dose of study drug (EOS/Early Termination Visit) are to be recorded on the appropriate Adverse Event CRF pages and in source documents.

Serious adverse events (SAEs), AESIs and pregnancies occurring during or within 30 days after the last dose of EPN-701 will also be reported in an expedited fashion, as described in Section 10.4. SAEs and AESI considered to be related to the study drug by the investigator, will be reported to the Sponsor even if they occurred after the protocol-specified reporting period (i.e., more than 30 days after the last dose of EPN-701). Follow-up of SAEs and AESIs will continue until resolution or until they reach a chronic/stable condition. In the unlikely event of a pregnancy reported during the study, the event should be followed until pregnancy outcome, i.e. birth or termination.

# 10.3.2 Adverse Event Recording Guidelines

Investigators should use correct medical terminology/concepts when recording adverse events on the Adverse Event eCRF. Colloquialisms and abbreviations should be avoided.

Only one adverse event term should be recorded in the event field on the Adverse Event eCRF.

The following guidelines should be observed when recording AEs:

- Preexisting medical conditions (present at the screening visit): should be recorded on the Medical History eCRF. A preexisting medical condition should be recorded as an AE only if the frequency or severity worsens during the study.
- Symptoms of the Disease Under Study: should not be recorded as AEs, as long as they are
  within the normal day-to-day fluctuation or expected progression of the disease. However,
  significant worsening of the symptoms should be recorded as an AE.
- Diagnosis vs Symptoms: Where possible, a diagnosis, rather than a list of symptoms, should be recorded. If a diagnosis has not been made, then each symptom should be listed individually. In addition to untoward AEs, unexpected benefits outside the investigational product indication should also be captured on the AE eCRF.
- Secondary AEs: In general, adverse events that are secondary to other events (e.g., clinical sequelae or cascade events) should be identified by their primary cause, except for severe or serious secondary events. If it is unclear as to whether the events are associated, each AE should be recorded separately on the Adverse Event eCRF.
- Persistent AEs (events that extends continuously between study visits): should only be recorded once, with the highest overserved/reported severity on the Adverse Event eCRF.
- Recurring AEs (events that resolves between study visits and subsequently recur): each recurrence should be recorded as a separate event on the Adverse Event eCRF.
- Abnormal laboratory values: All clinically significant laboratory test results must be reported
  as AEs. If a clinically significant laboratory abnormality is a sign of a disease or syndrome,
  only the diagnosis should be recorded on the Adverse Event eCRF.
- Abnormal ECG results: All treatment-emergent clinically significant ECG abnormalities must be reported as AEs.
- Adverse events associated with an incorrect administration (medication error or misuse) or overdose of the study drug should be recorded on the Adverse Event eCRF. Any incorrect administration of study drug or study drug overdose should be noted on the Study Drug Administration CRF and reported as a protocol deviation.
- Any occurrence of dialyzer clotting (assessed at each dialysis session) is to be recorded as an AE, using the term "clotting of extracorporeal circuit" or equivalent.

# 10.3.3 Assessment of Adverse Events

#### 10.3.3.1 Assessment of Severity

The medical assessment of AE severity is determined by using the following definitions:

 Mild: A type of AE that is usually transient and may require only minimal treatment or therapeutic intervention. The event does not generally interfere with usual activities of daily living.

- **Moderate:** A type of AE that is usually alleviated with specific therapeutic intervention. The event interferes with usual activities of daily living, causing discomfort but poses no significant or permanent risk of harm to the research subject.
- **Severe:** A type of AE that interrupts usual activities of daily living, or significantly affects clinical status, or may require intensive therapeutic intervention.

The severity of AEs must be assessed during the course of the event. An event that continues, but changes in severity over a period of time should be captured once on the AE eCRF form, with the highest severity reported though its duration. Worsening of pre-treatment events after initiation of investigational product, must be recorded as new AEs (for example, if a subject experiences mild intermittent dyspepsia prior to dosing of the investigational product, but the dyspepsia becomes severe and more frequent after first dose of investigational product has been administered, a new AE of severe dyspepsia [with the appropriate date of onset] is recorded on the AE eCRF).

# 10.3.3.2 Assessment of Causality

The causality assessment for each AE must be completed by the investigator. The investigator should use medical judgment, including knowledge of the subject, the circumstances surrounding the event, and evaluate any potential alternative causes when deciding whether there is a reasonable possibility that the event may have been caused by the investigational product. If there is no valid reason for suggesting a relationship, the AE should be classified as 'not related'. Otherwise, if there is any valid reason, even if undetermined or untested, for suspecting a possible cause-and-effect relationship between the investigational product and the occurrence of the AE, the AE should be assessed as 'related'. The causality assessment must be documented in the source document and the CRF.

Table 5 Guidance for the Assessment of Adverse Event Causality

Term	Relationship	Definition	
Definitively Related	Yes	A clinical event, including laboratory test abnormality that occurs in an apparent time sequence to the administration of the investigational product, is plausible pharmacologically, and cannot be explained by concurrent disease or other drugs or chemicals. Withdrawal of the drug (dechallenge) was followed by improvement or resolution of the event. Recurrence of symptoms on rechallenge (if performed) has occurred.	
Probably Related	Yes	A clinical event, including laboratory test abnormality, with a reasonable time sequence to the administration of the investigational product, unlikely to be attributed to concurrent disease or other drugs or chemicals. Withdrawal of the drug (dechallenge) was followed by improvement or resolution of the event. Rechallenge information is not required to fulfil this definition.	

Term	Relationship	Definition	
Possibly Related	Yes	A clinical event, including laboratory test abnormality, for which a time relationship with the administration of the investigational product may exist, but which could also be explained by concurrent disease or other drugs or chemicals. Information on drug withdrawal may be lacking or unclear.	
Unlikely Related	No	A clinical event, including laboratory test abnormality, with a doubtful temporal relationship to the administration of the investigational product, and in which other concomitant drugs, chemicals or the subject's underlying disease provide plausible explanations for the event.	
Not Related	No	The event can be readily explained by other factors such as the subject's underlying medical condition, concomitant therapy, or accident and no plausible temporal or biologic relationship exists between the investigational product and the event.	

The investigator's assessment of the relationship between the AE and the underlying condition (including hemodialysis) will also be recorded.

#### 10.3.3.3 Assessment and Documentation of Outcome

During the study period, resolution of AEs (with dates) should be documented on the AE eCRF and in the subject's medical record to facilitate source data verification.

The outcome of AEs must be recorded during the study on the CRF by selecting one of the following options:

- Recovered/Resolved
- Recovered/Resolved with Sequelae
- Ongoing, but reached chronic or stable condition at the last follow-up
- Fatal
- Unknown

#### 10.3.4 Adverse Event Follow-up Period

The investigator should follow each AE until the event has resolved to baseline or normal status, the event is assessed as stable by the investigator (no further improvement or worsening of the event is expected), the subject is lost to follow-up, or the subject withdraws consent. When appropriate, medical tests and examinations are performed so that resolution of event(s) can be documented.

Every effort should be made to follow all SAEs until a final outcome can be determined.

In the unlikely event of a pregnancy reported during the study, the event should be followed until pregnancy outcome, i.e. birth or termination.

#### 10.4 IMMEDIATE REPORTING REQUIREMENTS

# 10.4.1 Immediately Reportable Events

The investigator must report the following events to the Sponsor immediately (i.e., within 24 hours of becoming aware of the event), regardless of their relationship to study drug:

- SAEs
- AESIs
- Pregnancies
- Medication errors, misuses, and overdoses.

# 10.4.2 Reporting Requirements for SAEs and AESIs

# 10.4.2.1 Serious Adverse Event Reporting Timeframe

All SAEs and AESIs (regardless of their relationship to the study drug) occurring from the time the subject provided informed consent until 30 days after the last dose of study drug must be reported to the designated Pharmacovigilance Department within 24 hours of the first awareness of the event. Thereafter, any SAE(s) or AESI considered "related" to the study drug must be reported to the Pharmacovigilance Department within 24 hours of the first awareness of the event regardless of how much time has elapsed since the last dose of the study drug.

**Preferred method:** The investigator should report these events either by scanning and emailing the completed Serious Adverse Event/Adverse Event of Special Interest Reporting Form to the following e-mail address:

#### [contact]

**Alternative method:** The completed Serious Adverse Event/Adverse Event of Special Interest Reporting Form may be faxed to the following designated [contact]

**Attention: Epizon Safety** 

Reports should be accompanied by all relevant supplemental material. Receipt will be acknowledged in a timely manner via secure email.

Electronic data capture (EDC) is the primary source for entering SAE data documented on source documents. However, a back-up SAE Form (and Guidelines) for SAE reporting should be used for reporting to the Safety group within the SAE Reporting Guidelines in the event EDC is down or not accessible.

The investigator must also report new significant follow-up information for these events to the Sponsor immediately (i.e., no more than 24 hours after becoming aware of the information). New significant information may include any of the following:

Change in the event's outcome (including resolution)

- Change in the diagnosis
- Development of new signs or symptoms or significant worsening in the condition
- Significant new test results
- Change in causality based on new information
- Other significant information on the clinical course of the event.

Investigators must also comply with local requirements for reporting SAEs to the Institutional Review Board (IRB).

The onset date of the SAE is the date that symptoms of the event began, and the resolution date is the date the symptoms resolve, or the event is considered to have reached a chronic/stable condition.

Any SAE that results in the subject's death must have fatal checked as an outcome with the date of death recorded as the resolution date. For all other events ongoing at time of death that did not contribute to the subject's death, the outcome should be considered not resolved, without a resolution date recorded.

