# 9.6.2 Medical History and Demographic Data Collection

Details of the underlying condition (including ESRD and dialysis history), as well as general medical history (including clinically significant diseases or conditions, surgeries, and reproductive status), will be recorded at screening/baseline. Baseline complaints (symptoms or adverse experiences present prior to the first dose of study drug) will also be recorded as medical history.

Demographic data will include age, sex, and self-reported race/ethnicity.

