# 11.6.1 Adverse Events

All AEs will be coded using the current version of the Medical Dictionary for Regulatory Activities (MedDRA) and will be included in per-subject listings. In addition, treatment-emergent AEs

(defined as any AE with an onset between the first dose of the study drug and the last study visit, or any AE with an onset prior to first dose that increases in severity or frequency after the first dose of study drug) will be summarized in frequency tables, by MedDRA System Organ Class (SOC) and by Preferred Term (PT), regardless of the investigator-determined relationship to study drug. For each subject, if there are multiple occurrences of the same AE, the maximum severity reported will be used in the summaries.

Adverse events assessed as related to the study drug will be summarized in a similar manner. A summary of AEs by maximum severity grade will also be provided.

The following treatment-emergent AEs will also be summarized:

- Adverse events leading to permanent discontinuation of study drug (with or without withdrawal from the study)
- Adverse events leading to dose interruption
- Serious adverse events
- AFSIs
- Deaths.

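### An event with pre-dose symptoms that first becomes serious or fatal after the first dose, with no recorded rise in grade or frequency, is left out of the treatment-emergent tables, and two onset rules are not reconciled for such events

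*Combined protocol and SAP*

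**What the plan says.** Treatment-emergent status has two limbs in Section 10.1, repeated in the synopsis, Table 2, Section 11.6 and Section 11.6.1. The first is "any AE with an onset between the first dose of the study drug and the last study visit". The second is "any AE with an onset prior to first dose that increases in severity or frequency after the first dose of study drug".

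For serious events, Section 10.4.2.1 (in the text after the reporting addresses) sets the onset: "The onset date of the SAE is the date that symptoms of the event began". The note in Section 10.1 keeps seriousness apart from grade: "Severity and seriousness need to be independently assessed for each adverse event recorded on the eCRF".

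Two rules govern symptoms already present before dosing. Section 9.6.2 says: "Baseline complaints (symptoms or adverse experiences present prior to the first dose of study drug) will also be recorded as medical history". Section 10.3.3.1 says: "Worsening of pre-treatment events after initiation of investigational product, must be recorded as new AEs", each with an appropriate onset date. The sentence just before that one asks for a continuing event to be entered once, at its highest severity.

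Section 11.6.1 places its summaries of discontinuations, serious events and deaths under treatment-emergent events. Section 11.6 words the secondary endpoint as the frequency of serious events, without that restriction. All adverse events go into per-subject listings.

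**The concern.** Inclusion in the main safety tables depends on a date and, for events that started before dosing, on a change in grade or frequency. A serious event takes the date of its first symptom, which may precede Day 1. It then has to qualify through the second limb, and that limb does not mention seriousness or death. If the grade and frequency are recorded as unchanged, the event has no way into the tables, even though what made it serious happened on drug.

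The comparison itself may also be hard to make. Pre-dose complaints go to medical history, where no severity capture is stated. A continuing event entered once at its highest grade does not keep its pre-dose grade.

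This is a descriptive, first-in-human study in 15 subjects, so the safety tables are its main result. Any event lost through this gap makes them look more favourable.

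**Working it through.** The plan gives no figure to reproduce: Section 11.2 states that no formal sample size calculation was done, and all analyses are descriptive. The check applies the stated rules to each possible case.

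**Inputs.** The two-limb definition (Section 10.1); the symptom-date rule (Section 10.4.2.1); three severity grades with severe at the top (Section 10.3.3.1); fatal as an outcome, not a grade (Section 10.3.3.3); n = 15 (Section 11.2).

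**Step 1: first limb.** Symptoms began before Day 1, so under the symptom-date rule onset is pre-dose and the first limb is not met.

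**Step 2: second limb.** The condition in Section 11.6.1 is "any AE with an onset prior to first dose that increases in severity or frequency". With frequency unchanged, the non-decreasing grade pairs give:

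| Pre-dose grade | Grade after first dose | Treatment-emergent? |
|---|---|---|
| Mild | Moderate | Yes |
| Mild | Severe | Yes |
| Moderate | Severe | Yes |
| Mild | Mild | No |
| Moderate | Moderate | No |
| Severe | Severe | No |

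The three unchanged pairs stay out even if the event becomes serious or fatal. An event already severe before dosing cannot rise further. Death does not change the grade, and Section 10.4.2.1 uses the date of death as the resolution date, not the onset.

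**Step 3: the new-record rule.** Section 10.3.3.1 is triggered by worsening, and its worked example rises in both severity and frequency. It does not clearly reach an event that becomes serious at the same grade. Where it does apply, it calls for a new onset date, while Section 10.4.2.1 points to the first symptom. For one evolving event these can fall on either side of the first dose, and the protocol does not say which is used.

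**Step 4: tables affected.** The primary endpoint, and the Section 11.6.1 summaries of serious events, of deaths and (if the event led to stopping study drug) of discontinuations. The secondary endpoint as worded in Section 11.6 is not restricted, so the endpoint and its planned table do not match.

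**Step 5: size per subject.** 1/15 = 6.7 percentage points. The exact (Clopper-Pearson) 95% limits for x of n are the 0.025 quantile of Beta(x, n − x + 1) and the 0.975 quantile of Beta(x + 1, n − x):

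- 0/15 = 0%: lower limit 0, upper limit 1 − 0.025^(1/15) = 21.8%.
- 1/15 = 6.7%: lower limit 1 − 0.975^(1/15) = 0.2%, upper limit 31.9%.

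**The case against.** The strongest case against is that the protocol already catches most such events. Severe is defined as "A type of AE that interrupts usual activities of daily living, or significantly affects clinical status, or may require intensive therapeutic intervention", which would normally fit a hospitalization. A subject with mild symptoms before Day 1 who is admitted during dosing would usually rise in grade, meet the second limb, and fall under the new-record rule as well. Assessing seriousness separately does not stop the grade from rising. Inclusion criterion 3 requires clinical stability, and eligibility is reviewed again at Visit 1, so an event already severe before dosing is less likely. All of this stands and narrows the point.

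A reader might infer that any admission on drug with earlier symptoms drops out of the endpoint. The documents do not support that: it happens only when neither grade nor frequency is recorded as rising.

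A reader might also infer that the event is lost altogether. It is not. Section 10.4.2.1 requires serious events to be reported within 24 hours from consent onward, and Section 11.6.1 lists all adverse events. Only the summaries are affected.

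Nor do Sections 10.3.3.1 and 10.4.2.1 have to contradict each other. One can be read as saying when to open a new record, and the other as dating that record from its own symptoms. The protocol does not state that reading, so what remains is a missing reconciliation.

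**Conclusion.** The gap is real but narrow, and of minor priority. An event with pre-dose symptoms that first becomes serious or fatal after the first dose, with no recorded rise in grade or frequency (for example already severe, or still graded moderate), is excluded by a stated rule from the primary endpoint and the Section 11.6.1 summaries. Each such subject changes a frequency by 6.7 points, for example 0/15 (exact 95% CI 0 to 21.8%) instead of 1/15 (0.2 to 31.9%). This assumes a denominator of 15; if withdrawn subjects are replaced under Section 9.7.2.2, each step is slightly smaller.

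A reader might want a probability that this occurs. It would need an admission rate, the share of admissions with pre-dose symptoms, and the share of those with no rise in grade or frequency. The documents give none of these.

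A reader might also infer that dating from first symptoms always flatters the drug and should be replaced by the date of seriousness. The documents do not support that. Take symptoms on Day 27 and admission on Day 32, which is 18 days after a Day 14 last dose and so inside the 30-day reporting period. The symptom-date rule keeps this event in the treatment-emergent window, which closes at the last study visit on Day 29. Dating it to the admission would remove it, and the second limb could not bring it back because its onset was not pre-dose.

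**What to change.** 1. In Sections 10.1, 11.6 and 11.6.1, the synopsis and Table 2, extend the second limb so that a pre-dose event also qualifies if it first becomes serious or fatal after the first dose.
2. In Section 10.4.2.1, state that the new-record rule of Section 10.3.3.1 also applies to serious events that evolve from pre-dose symptoms.
3. In Section 11.6.1, tabulate all on-study serious events and deaths regardless of treatment-emergent status, to match the unrestricted endpoint in Section 11.6.
4. Leave the symptom-based onset in place. At most, record the date a seriousness criterion was first met as an additional field.

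The cost is a few lines of protocol and analysis text, one more table and, if wanted, one date field. Reported frequencies of serious and treatment-emergent events may be slightly less favourable. No dose, visit or clinical rule changes.
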